#### **5.4.3 Statistical Analysis**

All data were analyzed using SPSS25.0 statistical software. For continuous variables, median (minimum, maximum) was used for descriptive statistics; mean  $\pm$  standard deviation was used if the data followed a normal distribution and had homogeneous variance. Paired t-test was used for within-group comparisons, and two independent sample t-tests were used for between-group comparisons. Wilcoxon rank sum test was used for non-normal distributed data. For categorical variables, frequency (percentage) was used for descriptive statistics, and rates or composition ratios were used for comparisons between groups using the  $\chi^2$  test. Rank sum test was used for ordinal data. A value of  $P < 0.05$  was considered statistically significant.

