### **3 Research Objectives and Endpoints**

#### **3.1 Main purpose**

This study evaluated the efficacy of Naohuan Dan combined with Idebenone for treating MCI patients with Kidney-Deficient and Phlegm-Stasis syndrome. Changes in cognitive function, daily living abilities, depression levels, and Traditional Chinese Medicine clinical symptoms were assessed using relevant rating scales, and compared with the efficacy of Idebenone alone, demonstrating the advantages of combining traditional Chinese and Western medicine in treatment.

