#### **3.2 Main outcome**

The primary outcome measure for the study was the Mini-Mental State Examination (MMSE) scale scores [9], which were used to examine the cognitive function of the participants before and after therapy. A total score of 23-30 is considered to indicate normal cognitive function, 17-22 indicates mild cognitive impairment, 11-16 indicates moderate cognitive impairment, and 10 or below indicates severe cognitive impairment.

The clinical efficacy was evaluated based on the MMSE scale, and the efficacy was calculated by comparing the scores before and after the therapy. The following criteria were used to determine the efficacy: (i) Markedly effective:  $\geq 20\%$  improvement in MMSE score. (ii) Effective rate:  $\geq 12\%$  improvement in MMSE score. (iii) Ineffective:  $< 12\%$  improvement in MMSE score. The total efficacy was calculated as the sum of the markedly effective and effective rates.

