## **4 Research Population**

### **4.1 Inclusion criteria**

The following inclusion criteria were used: (1) diagnosis in line with Chinese medicine and Western medicine; (2) suitable for age 55-85 years old, gender is not limited; (3) a score between 21-26 on Mini-Mental State Examination (MMSE), 1 point for primary school education; (4) agree to take part in this experiment and sign the informed consent form.

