## **5 Research Design**

### **5.1 Intervention**

This retrospective, two-armed, single-center clinical observation evaluates the combination of Naohuan Dan and Idebenone for the treatment of MCI patients with Kidney Deficiency and Phlegm Stasis. Eligible patients were randomized using a random number table into a control group and a treatment group. The control group was given 30mg of Idebenone tablets three times a day after meals, while the treatment group was given Naohuan Dan in addition to Idebenone. The main components of the Naohuan Dan formula are Rehmannia glutinosa 25g, Codonopsis pilosula 20g, Acorus calamus 10g, Polygala tenuifolia 8g, Eucommia ulmoides 15g, and Poria cocos 12g, among other ingredients. The herbal granules were provided by Yifang Pharmaceutical Co., Ltd. The patients in both groups received corresponding treatments for underlying diseases such as hypertension and diabetes if present. One dose of herbal granules was administered daily with warm water in the morning and evening.

**Fig. 1** CONSORT flow chart.

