## 5.2 Research Calendar

The scale	MMSE	√															√
The MoCA scale		√															√
The ADL scale		√															√
The GDS scale		√															√
The TCM Syndrome score scale		√															√
Lab Test		√															√
Blood routine, Urine routine, Stool routine and Liver and Kidney function		√															√
Electrocardiogram		√															√
Adverse Events and Evaluation		√	√	√	√	√	√	√	√	√	√	√	√	√	√	√	√
Complete the Case Report Form		√	√	√	√	√	√	√	√	√	√	√	√	√	√	√	√

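### The between-arm test for MMSE is unadjusted and applied to an unspecified score; ANCOVA on baseline MMSE would cost almost nothing and may gain precision

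*Protocol*

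**What the plan says.** Section 5.4.3 sets the between-arm method for continuous outcomes: "two independent sample t-tests were used for between-group comparisons". The fallback is also unadjusted: "Wilcoxon rank sum test was used for non-normal distributed data". Baseline is explicit there only in the paired t-test within each arm. No section names a covariate or a regression model.

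Section 3.2 makes MMSE the primary outcome and describes scores "which were used to examine the cognitive function of the participants before and after therapy". The calendar in Section 5.2 ticks MMSE in its first and last columns, and Section 4.1 requires a baseline MMSE of 21 to 26 for entry. Baseline MMSE is therefore available for every patient.

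Section 5.4.3 does not say which score is compared between arms. Section 3.1 points towards change: "Changes in cognitive function, daily living abilities, depression levels, and Traditional Chinese Medicine clinical symptoms were assessed using relevant rating scales". Section 3.2 also grades response by percentage improvement in MMSE, with cut-offs at 12% and 20%.

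On allocation, Section 5.1 says "Eligible patients were randomized using a random number table into a control group and a treatment group", but opens by calling the study "This retrospective, two-armed, single-center clinical observation". Section 5.4.1 gives 64 patients with no effect size, SD or power, and disclaims strict hypothesis testing. Section 5.4.3 nevertheless sets a 0.05 significance threshold.

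**The concern.** A two-sample t-test on final scores treats the baseline slope as 0, and one on change scores treats it as 1. ANCOVA estimates the slope. If the true slope lies between 0 and 1, both t-tests leave in the comparison some variation that the baseline could explain.

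This matters because 64 patients is a small number with no power basis, while Section 3.1 sets out to show an advantage over Idebenone alone. Leaving the tested score unstated also leaves a choice between two analyses that can give different P values. Naming ANCOVA of the post-treatment score closes that choice, because with baseline as a covariate the arm effect is the same whether the outcome is the final score or the change.

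**Working it through.** **Inputs from the protocol.** N = 64 (5.4.1); significance at 0.05 (5.4.3), taken as two-sided; baseline MMSE 21 to 26 (4.1). The sample size has no design inputs, so there is no planned figure to reproduce.

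**Assumptions, not in the protocol.** 32 patients per arm; baseline-to-final correlation r = 0.3, 0.5 or 0.7; k = final SD / baseline SD = 1, 1.25 or 1.5.

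**Formulas.** With the final-score variance set to k² and the baseline variance to 1, the variance of the arm contrast is proportional to:
- final-score t-test: k²
- change-score t-test: k² + 1 − 2rk
- ANCOVA: k²(1 − r²), times (N − 3)/(N − 4) = 61/60 = 1.017 for estimating the slope

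**ANCOVA against a final-score t-test**, 1.017 × (1 − r²):
- r = 0.3: 1.017 × 0.91 = 0.93
- r = 0.5: 1.017 × 0.75 = 0.76
- r = 0.7: 1.017 × 0.51 = 0.52

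**ANCOVA against a change-score t-test**, 1.017 × k²(1 − r²)/(k² + 1 − 2rk):

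| k | r = 0.3 | r = 0.5 | r = 0.7 |
|---|---|---|---|
| 1 | 0.66 | 0.76 | 0.86 |
| 1.25 | 0.80 | 0.91 | 1.00 |
| 1.5 | 0.89 | 0.98 | 1.01 |

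For example, at k = 1.25 and r = 0.3: 1.5625 × 0.91 / (2.5625 − 0.75) = 0.784, and 0.784 × 1.017 = 0.80. The change score is optimal when the true slope rk equals 1. The ratio is then 1.017, which is the worst case.

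**Simulation on an MMSE-like scale.** Integer baseline uniform on 21 to 26; final score rounded and capped at 30; 32 per arm; assumed difference 1.3 points; 20,000 trials per scenario. Power in %:

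| Slope, mean change, error SD | t, final | t, change | ANCOVA | Rank ANCOVA | ANCOVA − t, change |
|---|---|---|---|---|---|
| 0.4, 1, 1.5 | 86.8 | 79.2 | 91.3 | 90.0 | +12.1 |
| 0.4, 2, 2 | 66.6 | 59.9 | 70.4 | 68.5 | +10.5 |
| 0.7, 1, 1.5 | 75.1 | 88.8 | 91.4 | 89.8 | +2.6 |
| 0.7, 2, 2 | 57.5 | 67.1 | 69.8 | 67.8 | +2.7 |
| 0.7, 2, 2.5 | 44.5 | 49.2 | 51.1 | 49.8 | +1.9 |
| 1, 1, 1.5 | 60.4 | 91.6 | 91.2 | 89.2 | −0.4 |
| 1, 2, 2 | 47.5 | 70.0 | 69.4 | 67.4 | −0.6 |

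Against the final-score t-test, ANCOVA gains 3.8 to 30.8 points. Against the change-score t-test, five of the seven scenarios lie between −0.6 and +2.7 points. Under the null, every test in the table, and the rank sum test on either score, rejected in 4.7 to 5.3% of trials.

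**The case against.** The strongest objection is that the benefit may be negligible. Sections 3.1 and 3.2 lean towards change from baseline, and a change score already uses the baseline. Limiting entry to 21 to 26 narrows the baseline spread but not the final spread, which favours k above 1, where ANCOVA gains least over a change score. A uniform baseline also gives more spread than a centred one. With assumed centred weights of 1:2.5:4:4:2.5:1, the ANCOVA-to-change variance ratio across the seven scenarios runs from 0.80 to 1.02. This objection stands: the large gains belong to final-score tests or to low slopes, and no input in the protocol says which case applies.

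A reader might infer more than the protocol supports in four ways.
- *That baseline is ignored altogether.* This would be true only of a final-score test, which Section 5.4.3 does not specify. The percentage-improvement grading in Section 3.2 also uses baseline.
- *That the planned tests are invalid.* Under the stated randomization they are not; null rejection stays near 5%.
- *That a bounded integer scale calls for a rank-based fallback, adjusted or not.* In the scenarios above ordinary ANCOVA has higher power than rank ANCOVA in all seven, with no loss of error control. A switch triggered by the data would add another analyst choice.
- *That ANCOVA would rescue a non-random comparison.* If the retrospective label in Section 5.1 means that allocation was not random, the precision argument no longer applies as it stands, and ANCOVA would remove only the imbalance carried by baseline MMSE.

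**Conclusion.** The point holds as a low-cost improvement in precision. It is fair to raise against the protocol alone, because Section 5.4.3 itself fixes the unadjusted tests and leaves the tested score open.

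The absence of adjustment is certain. The size of the benefit is not, since the allocation ratio, r, k and the 1.3-point effect are all assumed. Within those assumptions the variance falls by about 7 to 48% against a final-score t-test. Against a change-score t-test the result runs from a 34% reduction to a loss of about 1%, and the loss cannot be expected to exceed about 1.7%. A cost that small against a possible material gain justifies the change, but no stated figure in the protocol is contradicted.

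**What to change.** In Section 5.4.3, make the between-arm analysis of MMSE an ANCOVA of the post-treatment score on arm and baseline MMSE, and report the adjusted mean difference with its 95% CI. Do the same for MoCA, ADL, GDS and the TCM syndrome score, each with its own baseline. Keep ordinary ANCOVA as the single main analysis for MMSE, with no switch to a rank test based on the observed data; a rank-based analysis may be added as a sensitivity analysis only.

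If outcomes have already been seen, as the retrospective description may imply, label the ANCOVA post hoc and report it alongside the planned t-test, stating which score that t-test uses.

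The cost is a few sentences and one degree of freedom. No new data are needed, and SPSS fits the model. The change does not restore pre-specification or repair non-random allocation. How patients lost to follow-up are handled is a separate issue: Section 5.4.2 carries the last observation forward and Section 7.3 excludes them, and the two sections need to be reconciled in their own right.

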### **3.3 Secondary outcomes**

The secondary outcome measures for the study included various scales and serological indicators. The scales used in the study were the Montreal Cognitive Assessment (MoCA) scale, the ADL scale, the Geriatric Depression Scale (GDS) and the TCM syndrome score scale.

The MoCA scale is a widely used screening tool for detecting mild cognitive impairment. It assesses various cognitive domains such as attention, memory, visuospatial skills, language, and orientation. The total score on the MoCA scale is 30, and a score of 26 or higher is considered to indicate normal cognitive function.

The ADL scale is used to assess the participants' ability to perform daily living activities. The total score on the ADL scale is 100 points.

The GDS scale is a self-report assessment tool used to detect and measure the severity of depression in older adults. The total score on the GDS scale is 30 points.

The TCM clinical symptoms of the participants were evaluated using the TCM syndrome score scale. This tool assesses the severity of specific TCM symptoms and divides them into four grades: none, mild, moderate, and severe, with 0, 2, 4, and 6 points (for main symptoms) or 0, 1, 2, and 3 points (for secondary symptoms), respectively. The total score was calculated before and after the therapy to determine the effectiveness of the treatment.

Blood samples were collected from the participants before and after the therapy via cubital venipuncture. Enzyme-linked immunosorbent assay (ELISA) was used to determine the serum levels of neuron-specific enolase (NSE), interleukin-8 (IL-8) and tumor necrosis factor-alpha (TNF- $\alpha$ ) using the Reader M3 multi-function microplate reader.

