### 5.4 Statistical Analysis

#### 5.4.1 sample size

This study is a retrospective, two-arm study with a fixed sample size and no strict hypothesis testing. A total of 64 participants were enrolled in this study.

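### Section 5.4.3 names only an independent-samples rank test for non-normal and ordinal data, so read literally its before/after comparisons within each group would ignore the pairing

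*Protocol*

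**What the plan says.** For normally distributed continuous data, Protocol section 5.4.3 assigns a test to each kind of comparison: "Paired t-test was used for within-group comparisons, and two independent sample t-tests were used for between-group comparisons".

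For other continuous data it names one test and does not separate the two kinds of comparison: "Wilcoxon rank sum test was used for non-normal distributed data". For ordinal outcomes it adds: "Rank sum test was used for ordinal data". The significance rule is "A value of $P < 0.05$ was considered statistically significant". No signed-rank, sign or other paired rank test is named anywhere in the Protocol.

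The outcomes are repeated measurements on the same people. Section 3.2 introduces the MMSE scores as those "which were used to examine the cognitive function of the participants before and after therapy". Section 3.3 says of the serum markers: "Blood samples were collected from the participants before and after the therapy via cubital venipuncture". The calendar in section 5.2 marks each scale and the laboratory tests at two time points.

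**The concern.** The parametric sentence recognises that before/after data are paired; the non-parametric sentences do not. The rank sum test treats its two sets of values as coming from different people. Applied to one group's before and after values, it uses a standard error that leaves out the correlation between them.

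The non-normal branch could well be used. Section 5.4.3 describes continuous variables by median and range, and by mean and SD only if normality and equal variance hold. Entry confines baseline MMSE to 21-26 (section 4.1). MoCA, ADL and GDS have fixed maximum scores, and TCM symptoms are graded in four steps (section 3.3). The Protocol does not report the distribution of any outcome, so which outcomes would take this branch is unknown.

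At stake are the within-group P values for those outcomes. A real change from baseline could be reported as non-significant because of the test chosen.

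**Working it through.** **Is there a figure to reproduce?** No. Section 5.4.1 fixes the sample size without a power calculation, and the Protocol gives no SD, effect size or before/after correlation.

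**Inputs from the Protocol**
- Total sample size: "A total of 64 participants were enrolled in this study" (section 5.4.1).
- Significance level 0.05 (section 5.4.3).

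**Assumptions, not in the Protocol**
- 64 / 2 = 32 patients per group, since no allocation ratio is given.
- Two-sided testing.
- Before/after correlation ρ from 0.3 to 0.8.
- A true shift of 0.4 SD for the power figures.

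**Step 1: actual type I error of rank sum on pairs, by formula.** The rank correlation implied by ρ under bivariate normality is r = (6/π)·arcsin(ρ/2). The variance of the difference in ranks shrinks by the factor (1 − r), but the test does not know this. The actual size is therefore about 2·[1 − Φ(1.96/√(1 − r))].

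| ρ | r | √(1 − r) | 1.96/√(1 − r) | actual size |
|---|---|---|---|---|
| 0.3 | 0.288 | 0.844 | 2.32 | 0.020 |
| 0.5 | 0.483 | 0.719 | 2.72 | 0.0064 |
| 0.7 | 0.683 | 0.563 | 3.48 | 0.0005 |
| 0.8 | 0.786 | 0.463 | 4.24 | 0.00002 |

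**Step 2: simulation with 32 pairs and two data shapes.** One shape is skewed (lognormal, with the shift on the log scale). The other is whole-number scores from a rounded normal distribution with SD 1.7, about the SD of scores spread evenly over 21-26: √((6² − 1)/12) = 1.71. Each entry is rank sum / signed-rank.

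| ρ | Type I error, lognormal | Type I error, rounded | Power, lognormal | Power, rounded |
|---|---|---|---|---|
| 0.3 | 0.020 / 0.048 | 0.025 / 0.054 | 0.31 / 0.41 | 0.30 / 0.43 |
| 0.5 | 0.009 / 0.049 | 0.0085 / 0.048 | 0.28 / 0.51 | 0.28 / 0.57 |
| 0.7 | 0.0008 / 0.051 | 0.0013 / 0.045 | 0.24 / 0.73 | 0.24 / 0.77 |
| 0.8 | 0.0003 / 0.055 | 0.0003 / 0.047 | 0.22 / 0.88 | 0.21 / 0.90 |

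The formula and both simulations agree in direction and closely in size. Signed-rank stays near 5% throughout.

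**Step 3: direction.** In the lognormal simulation rank sum has size 0.053 at ρ = 0 and 0.076 at ρ = −0.3. False positives rise only if before and after values are negatively correlated, which is not to be expected for repeated measurements on one patient.

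**Step 4: which ρ for MMSE?** Restricting the baseline range lowers the correlation. If the unrestricted correlation were 0.7, with mean 24 and SD 2.5 to 4 (all assumed), selecting baseline scores of 21-26 would bring it down to about 0.51 to 0.37. The rows for 0.3 and 0.5 are therefore the more relevant ones for the primary scale: a power loss of about 10 points (0.41 − 0.31) to 29 points (0.57 − 0.28).

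**The case against.** The strongest reply is that the Protocol never says rank sum is used within groups. The sentence follows directly on the between-group t-test and can be read as the fallback for that test alone, where it is correct. The paired rank test would then merely be unnamed, a detail that could sit in an analysis plan not at hand. It may also be loose wording for Wilcoxon tests in general. Either is possible, and a reader should not infer that a wrong within-group test is known to have been run. But the sentence carries no such limit: it covers non-normal data as a whole, and rank sum is the only rank test named, twice. If signed-rank was in fact used, the text misdescribes the analysis and still needs correcting.

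The other replies limit the point, and they stand:
- The main purpose (section 3.1) is comparison with Idebenone alone, and rank sum is valid for that.
- Within-group change cannot separate a drug effect from practice, placebo or time effects, and section 5.4.1 disclaims strict hypothesis testing.
- The error makes a false claim of improvement less likely.
- The largest power losses rest on correlations of 0.7 to 0.8, which the Protocol does not supply.

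**Conclusion.** The point holds as a wrongly named test of limited reach. Taken literally, section 5.4.3 applies an independent-samples test to paired before/after data whenever an outcome is non-normal or ordinal. Under positive correlation the within-group P values are too large.

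The size depends on assumptions. With 32 pairs and correlation 0.3 to 0.8, actual type I error is about 2% down to below 0.1% instead of 5%. The loss of power for a 0.4 SD shift runs from about 10 percentage points to nearly 70. That the P values are too large holds at every positive correlation tried; how much too large is not established for any particular outcome.

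Three stronger conclusions might be inferred, and the Protocol supports none of them:
- *The treatment comparison is invalid.* It is not: those groups are independent, and rank sum suits them.
- *The plan inflates false positives.* With positive correlation it does the opposite.
- *The between-group analysis must move to change from baseline.* Section 5.4.3 does not say which score is compared between groups, and that is a separate question which this defect does not settle.

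**What to change.** Replace the sentences on non-normal and ordinal data in section 5.4.3 with: *For non-normal or ordinal data, the Wilcoxon signed-rank test is used for within-group (before/after) comparisons, and the Wilcoxon rank sum test is used for between-group comparisons only.*

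Make no other change to the between-group analysis on account of this point. Because the section is written in the past tense, check which test was actually run, and repeat with signed-rank any within-group result obtained with rank sum.

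The cost is one rewritten passage and, at most, a few repeated tests on data already collected for the same patients. No new data are needed.

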## 1 Program Summary

This study conducted a retrospective analysis of 64 patients with mild cognitive impairment of the kidney deficiency phlegm and stasis type who underwent treatment with Naohuan Dan combined with Idebenone. The patients' cognitive function was evaluated using the Mini-Mental State Examination (MMSE) and the Montreal Cognitive Assessment (MoCA) before and after treatment. Daily living abilities were assessed using the Activities of Daily Living (ADL) scale, depression status was evaluated using the Geriatric Depression Scale (GDS), and the severity of Traditional Chinese Medicine (TCM) syndrome was assessed using the TCM diagnostic scale. Peripheral blood from the patients was also collected for analysis of neuron-specific enolase (NSE) and inflammatory factors. The aim was to evaluate the safety and feasibility of using Naohuan Dan combined with Idebenone for the treatment of mild cognitive impairment of the kidney deficiency phlegm and stasis type.

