designed a clinical study to evaluate the efficacy and safety of the combination of Naohuan Dan combined with Idebenone for the treatment of MCI, by assessing relevant cognitive function rating scales and TCM syndrome scores. This study aims to provide valuable information for the integration of TCM and Western medicine in the treatment of MCI.

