### **3.4 Safety Index**

Before and after treatment, the patient's elbow vein blood is collected for blood routine, urine routine, stool routine, and liver and kidney function tests. The patient's electrocardiogram is also monitored, and any adverse reactions after medication are observed and treated accordingly.

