# **8 Adverse Events and Unexpected Events**

## **8.1 Adverse event**

Adverse events (AE) refer to all adverse medical events that occur in subjects after receiving the investigational drug. They can manifest as symptoms, signs, diseases, or laboratory abnormalities, but are not necessarily causally related to the investigational drug.

The grading of adverse events is as follows:

Grade 1: Mild; asymptomatic or mild symptoms; only clinical or diagnostic manifestations; no intervention required;

Grade 2: Moderate; requires minimal, partial, or non-invasive intervention; restricts appropriate age daily activities;

Grade 3: Severe or significant medical events that require drug treatment, but do not immediately threaten life; hospitalization or prolonged hospitalization; disability; restricts activities of daily living (ADLs);

Grade 4: Life-threatening consequences; requires urgent intervention;

Grade 5: Death related to AE.

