## **9 Data collection and management**

All patient clinical testing reports in this project strictly adhere to the legally prescribed national unit of measurement. The patient testing and follow-up records must be complete, including the date, recorded items, results, and normal value ranges, among other information, and must be signed by relevant personnel. Clinical case data and follow-up data are recorded and collected by trained and professional data

collection and management personnel, and reviewed and confirmed for accuracy by the team leader before being entered into the database.

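### Safety is a stated aim, but the only between-arm method for event rates is a generic chi-square test at P<0.05, and a non-significant result from it cannot by itself support a comparative safety conclusion

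*Protocol*

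**What the plan says.** Two places in the Protocol make safety an aim. Section 1 (Program Summary) states: "The aim was to evaluate the safety and feasibility of using Naohuan Dan combined with Idebenone". Section 2 (Introduction) says that the investigators "designed a clinical study to evaluate the efficacy and safety of the combination". Section 3.1 (Main purpose) names efficacy only.

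Section 5.4.1 gives the size without a power target: "A total of 64 participants were enrolled in this study". It describes that size as fixed and disclaims strict hypothesis testing. Section 5.1 gives the allocation method, "Eligible patients were randomized using a random number table into a control group and a treatment group", but no ratio or arm sizes.

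Section 5.4.2 defines a Safety Analysis Set and attaches no method to it. Section 5.4.3 covers all data with one set of generic rules. Categorical variables are described by frequency and percentage, and "rates or composition ratios were used for comparisons between groups" with the chi-square test. Ordinal data go to a rank sum test, and the threshold is P<0.05. No confidence interval, margin or rule specific to safety appears. Section 8.1 defines adverse events as occurrences after the study drug that may take many forms "but are not necessarily causally related to the investigational drug".

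**The concern.** If the arms are to be compared on the proportion of patients with an adverse event, section 5.4.3 as written yields two percentages and a P value. The P value answers only whether a difference has been demonstrated. A safety aim asks something else: how large an excess in the combination arm the data can rule out. In a trial of 64 people, a non-significant test is the likely result even when the combination doubles an event rate of modest size. Percentages without an interval do not show that limitation. At stake is how the safety result is read: the same data can look reassuring as a P value and plainly inconclusive as an interval.

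**Working it through.** The Protocol gives no power, effect size or event rate, so there is no figure of its own to reproduce.

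**Inputs**
- Total N = 64 (Protocol 5.4.1).
- Two arms (5.1). The arm sizes are not stated, so 32 per arm is an assumption.
- Test and threshold: chi-square, P<0.05 (5.4.3). No continuity correction or Fisher rule is stated.
- Event rates: none stated. All rates below are illustrative assumptions.

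**Step 1: power.** Let X ~ Bin(32, p1) and Y ~ Bin(32, p2). Power is the sum of P(X=i)·P(Y=j) over all 33 × 33 tables in which the Pearson chi-square test gives P<0.05.

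| Control v combination | Exact power | Non-significant |
|---|---|---|
| 2% v 4% | 2% | 98% |
| 5% v 10% | 11.5% | 88.5% |
| 10% v 20% | 20.5% | 79.5% |
| 15% v 30% | 30.5% | 69.5% |
| 20% v 40% | 42.4% | 57.6% |
| 30% v 60% | 71.3% | 28.7% |

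A tripling from 10% to 30% has power 53.2%.

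**Step 2: sensitivity of the 10% v 20% row.**
- Other arm sizes (control/combination): 30/34 gives 18.4%, 34/30 gives 20.7%, 28/28 gives 18.3%.
- With the Yates correction or Fisher's exact test at 32 per arm, power is 10.9%.
- By the normal approximation, 80% power would need 199 per arm.

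**Step 3: validity of the chi-square approximation.** With equal arms, the smallest expected count is (total events)/2, so it falls below 5 when there are 9 or fewer events in all. Under the assumed rates this happens in 50% of samples at 10% v 20%, 98% at 5% v 10% and nearly all at 2% v 4%. It is uncommon at higher rates (6% of samples at 15% v 30%).

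**Step 4: what an interval would show.**
- 3/32 in each arm: the Wilson limits for 3/32 (9.4%) are 3.2% and 24.2%. The Newcombe 95% limits for the difference are ±√[(0.0938−0.0324)² + (0.2422−0.0938)²] = ±0.161. The P value is 1, yet the interval runs from about −16 to +16 percentage points.
- 3/32 v 9/32: chi-square = 64·(3·23 − 9·29)² / (32·32·12·52) = 2,359,296 / 638,976 = 3.69, P = 0.055. A threefold observed excess is classed as not significant. The Newcombe interval is about −1 to +37 points.
- 0/32 in one arm: the exact two-sided 95% upper limit is 1 − 0.025^(1/32) = 10.9%.

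**The case against.** The best defence is that section 5.4.3 is a generic rule that never mentions adverse events. It also serves the response rates in section 3.2, and it plans frequencies and percentages beside the test. The stated main purpose is efficacy, strict hypothesis testing is disclaimed, low power for adverse events is ordinary at this size, and fuller safety tables may be in a SAP that is not shown.

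Most of this stands and limits the point. The absence of detailed safety tables is not a finding, and nobody should ask for a larger trial. It does not remove the point, because the Protocol itself names a method for comparing rates and sets a significance threshold, and that method does not suit an aim it declares twice. Disclaiming strict testing favours estimation over a P value.

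A reader might infer three stronger things that the Protocol does not support:
- **That the investigators will report P>0.05 as proof of safety.** No section says so.
- **That only causally attributed events will be counted, so attribution could lower the count in one arm.** Section 3.4 says "any adverse reactions after medication are observed and treated accordingly", which is not a counting rule. The calendar in 5.2 schedules adverse events throughout, and 8.1 defines them regardless of cause.
- **That comparing group averages will hide individual abnormal laboratory values.** Section 8.1 lets laboratory abnormalities enter as adverse events, and section 9 requires records "including the date, recorded items, results, and normal value ranges".

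**Conclusion.** The point holds as a matter of method for the between-arm safety comparison. A non-significant chi-square test cannot by itself support a comparative safety conclusion here. For a doubled event rate the test would miss the excess in roughly 29% to 98% of trials, depending on the background rate, and in about four out of five at 10% v 20%. The small expected counts likely at or below those rates also make the chi-square approximation doubtful there.

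The size rests on two assumptions: 32 per arm, and illustrative event rates. The result changes little with arm size (18% to 21% power at 10% v 20% for the splits checked) and a great deal with the event rate. It would be too strong to say that the trial can support no safety conclusion at all: the planned frequencies and percentages permit a descriptive summary.

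**What to change.** In section 5.4.3, add a safety paragraph for the Safety Analysis Set. The main safety output should be, per arm, the number and percentage of patients with any adverse event as defined in 8.1, with an exact (Clopper-Pearson) 95% CI. Give the risk difference, combination minus control, with a score-based 95% CI such as Newcombe's, in place of the chi-square P value. State that P>0.05 is not evidence of safety.

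This uses data already scheduled for collection and needs no more patients. It costs a few lines of wording and one extra table. The safety statement becomes more cautious, because the interval will usually be wide at this size.
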